promoting completion of the 3-dose series due to their convenient locations and longer hours of operation.^{30, 31} 5) We will be recruiting participants directly from the community and thus will be able to *extend the reach of the intervention to those individuals who might not normally see a physician.*^{32, 33} Together, these elements reflect a novel approach to promoting HPV vaccination among young MSM.

Preliminary Data

HPV vaccination among young MSM. To inform the proposed project, Drs. [name], [name], and [name] conducted a pilot study to identify barriers and facilitators to HPV vaccine uptake among young MSM.⁸ We recruited a national sample of 336 MSM aged 18-26 to complete an online survey. 21% had received ≥ 1 dose of HPV vaccine. Provider recommendation was the strongest predictor of uptake such that MSM with a recommendation were over 40 times more likely to have been vaccinated. We also observed disparities in uptake, with lower rates among 21-26 year-olds (vs. 18-20), Latinos (vs. Whites), and HIV-negative (vs. HIV-positive) men. Primary barriers to uptake included lack of information about HPV and the vaccine, lack of provider recommendation, and not having disclosed their sexual identify to their provider.

Reducing barriers to HPV vaccination. In previous work (R03CA138069), [name] identified primary barriers to HPV vaccine uptake among young adult women aged 18-26³⁴ and demonstrated that tailoring intervention materials to women's perceived barriers increased their intentions to receive HPV vaccine.³⁵ Intervention materials addressed common barriers to uptake including lack of information about HPV and the vaccine, concerns about side effects and vaccine safety, low perceived need due to not being sexually active or in a committed relationship, disliking shots, and vaccine cost. In the proposed RCT, we will use a *targeted approach*^{36, 37} such that treatment messages will be specifically designed for MSM (e.g., provide tips to address common and unique barriers to HPV vaccine uptake among young MSM).

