11.0 Data and Specimen Management

Analysis Strategy

Intervention feasibility will be computed as outlined above and summarized in a CONSORT map. Acceptability of the intervention will be assessed with descriptive statistics for the closed-ended items and with the same qualitative approach used for the online FG data for the open-ended items. Intervention efficacy will be assessed using an intent-to-treat approach. T-tests and chi-square analyses will be used to compare baseline characteristics of participants in the treatment vs. control condition. Separate chi-square analyses will be conducted for HPV vaccine initiation (receipt of ≥ 1 dose) and completion (receipt of 3 doses) to assess effects of treatment. Secondary analyses will examine potential differences in IMB constructs at the end of Phase 1 by treatment arm and assess whether they mediate effects of t2p on vaccine uptake. Following [name],³⁴ we will also conduct a detailed analysis of barriers to vaccine uptake among participants who did not get vaccinated over the course of the study to inform additional modifications for the large-scale trial.

Power Analysis

Based on previous studies,^{14, 41, 43, 54} we hypothesize that 18-21% of treatment arm participants will receive their 1st dose of HPV vaccine, compared to 6-8% of control arm participants. The comparison of outcomes between arms, with two-sided alpha = 0.05, will have $> 80\%$ power for all scenarios with N=192 per condition. Based on previous

PROTOCOL TITLE: txt2protect

studies with similar samples (G2G, Keep It Up! [KIU!])^{38, 49} and retention rates as high as 85-95% with follow-ups as long as one year, we anticipate an attrition rate of 5-20%. Using the most conservative estimate (20%) we will enroll 230 participants per arm to account for attrition.

Steps to Maintain Data Security and Confidentiality

Participant privacy and data will be carefully protected. Online surveys will be conducted online using a secure web-based application (REDCap).

To maintain privacy in the online focus groups, all participants will be asked to use pseudonyms rather than their real names, and to refrain from mentioning others by name. This will help to ensure openness. If any personal information is inadvertently disclosed, names or other identifying information will be redacted from the focus group transcripts.

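### The barrier analysis covers only men who stayed unvaccinated, so it can describe their barriers but cannot show which barriers are related to non-uptake

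*Combined protocol and SAP*

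**What the plan says.** Section 11.0, Analysis Strategy, following an earlier study of perceived barriers to HPV vaccination, says "we will also conduct a detailed analysis of barriers to vaccine uptake among participants who did not get vaccinated over the course of the study". The stated use is "to inform additional modifications for the large-scale trial". The section names no vaccinated comparison group, contrast or model for this analysis, and no rule for choosing which barriers to act on.

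The same paragraph plans to compare IMB constructs between arms at the end of Phase 1 and to "assess whether they mediate effects of t2p on vaccine uptake". That analysis uses vaccinated and unvaccinated men, but barriers are not named in it.

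Section 2.0, Preliminary Data, reports the team's national survey: "Provider recommendation was the strongest predictor of uptake such that MSM with a recommendation were over 40 times more likely to have been vaccinated". That result relates a factor to uptake, and so needed vaccinated men.

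**The concern.** An analysis restricted to one level of the outcome carries no information about what separates the two levels. Suppose, purely as an illustration, that 60% of unvaccinated men hold a concern. If 60% of vaccinated men hold it too, it does not distinguish the groups. If only 30% of vaccinated men hold it, it does. The planned analysis gives the same figure, 60%, in both cases.

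This matters because barriers are central to the intervention. Section 9.0 has the treatment messages written around the barriers attached to each IMB component, and each treatment module carries tips for overcoming them. Findings about barriers therefore feed into message content for the next trial. If frequency among non-vaccinators is read as evidence that a barrier holds back uptake, effort may go to common concerns that have little to do with uptake.

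The trial is well placed to do better. All RCT participants must be unvaccinated at entry, by self-report and registry check (sections 3.0 and 28.0), so baseline answers precede any trial dose. Vaccination status is checked in I-CARE for all of them at the end (sections 8.0 and 9.0).

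**Working it through.** **Inputs**, all from section 11.0, Power Analysis: initiation of "18-21% of treatment arm participants will receive their 1st dose of HPV vaccine, compared to 6-8% of control arm participants"; test "with two-sided alpha = 0.05"; and a claim of more than 80% "power for all scenarios with N=192 per condition". No figure is attached to the barrier analysis itself. I take vaccinated to mean at least one dose.

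**Step 1: reproduce the plan's power.** I used the normal approximation for two proportions, with pooled variance under the null and no continuity correction:

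power = Φ{[|pT − pC| − 1.96·√(2p̄(1 − p̄)/n)] / √[(pT(1 − pT) + pC(1 − pC))/n]}

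For 18% vs 8% with n = 192 and p̄ = 0.13, this is (0.100 − 0.0673)/0.0339 = 0.964, so power is 83.3%. The other scenarios give 95.4% (18% vs 6%), 99.2% (21% vs 6%) and 95.4% (21% vs 8%). The claim holds, so the plan's rates and sample size can be carried forward.

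**Step 2: who is in the barrier analysis.** Vaccinated = n(pT + pC); unvaccinated = 2n minus that.

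| Per arm | Rates | Vaccinated | Unvaccinated |
|---|---|---|---|
| 192 | 18% / 6% | 46.1 | 337.9 |
| 192 | 21% / 8% | 55.7 | 328.3 |
| 230 | 18% / 6% | 55.2 | 404.8 |
| 230 | 21% / 8% | 66.7 | 393.3 |

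The planned analysis uses none of the vaccinated men. Its outcome variance is zero, so no difference, odds ratio or correlation with uptake can be computed. It can estimate prevalence among the unvaccinated. At 50% endorsement and 338 men the 95% half-width is 1.96·√(0.25/338) = 5.3 points.

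**Step 3: precision if the vaccinated men are included.** At an assumed 50% endorsement in both groups, the half-width of the difference is 1.96·√(0.25/n₁ + 0.25/n₀):

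- 46 vs 338: 15.4 points
- 56 vs 328: 14.2 points
- 230 per arm (55 vs 405; 67 vs 393): 14.1 and 13.0 points

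Stratifying by arm costs little. With common variance 0.25 the half-width is 0.98/√Σ(n₁n₀/N), summed over arms. At 18% / 6% the terms are 34.6 × 157.4/192 = 28.3 and 11.5 × 180.5/192 = 10.8, giving 15.7 points. At 21% / 8% they are 31.9 and 14.1, giving 14.5 points.

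**Step 4: detectable gap.** This uses the same power formula with unequal groups (unadjusted, two-sided 0.05, 80% power) and an assumed endorsement among unvaccinated men:

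| Per arm | 30% endorsement | 50% endorsement |
|---|---|---|
| 192 | 17-18 points | 20-22 points |
| 230 | 16-17 points | 18-20 points |

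Check at 46.1 vs 337.9, with 28.5% vs 50%: pooled SE 0.0784, unpooled SE 0.0718, and (0.215 − 0.1537)/0.0718 = 0.85, so power is 80%.

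**The case against.** A descriptive account of why men remained unvaccinated after nine months of messages is a legitimate question. Vaccinated men cannot give reasons for not vaccinating, and the plan makes no predictive or causal claim for this analysis. That stands, and it is why the analysis should be kept.

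A reader might infer that this analysis alone decides how the messages change. The text says only that it will inform changes. The national survey, the Aim 1 focus groups (two of the four with vaccinated men), the local survey and interviews, and the open-ended acceptability items also bear on content. However, the survey and the Aim 1 work precede the RCT, and the acceptability items ask about the programme. None of them relates barriers to uptake within the trial.

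A reader might also infer that barriers will be ranked by endorsement and the wrong ones chosen. The documents give no ranking or selection rule, no list of barriers and no endorsement rates, and the method is deferred to a cited paper. A misranking rate would therefore reflect whatever rule and rates were assumed. Ranking by differences would not be immune either: it also produces a leading set when nothing is related to uptake.

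The mediation analysis is the best candidate for covering the gap, since the protocol ties barriers to IMB components. If barrier items sit inside the IMB measures, it relates constructs containing them to uptake. Its question is whether those constructs carry the arm effect, and no barrier-by-barrier result is planned.

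**Conclusion.** The limitation is real but modest. As written, the analysis can give the prevalence of each barrier among non-vaccinators, to within about 5 points. It cannot show which barriers are related to non-uptake, and no other planned analysis reports that item by item. This follows from the restriction itself and needs no assumed rates.

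It affects one exploratory analysis in a pilot. The initiation and completion comparisons do not depend on it, and the documents do not support saying that the messages will be changed wrongly.

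The gain from including the 46-56 vaccinated men (55-67 if all 460 contribute) is also limited: only gaps of roughly 16-22 points are detectable for a single item. These sizes rest on the plan's hypothesised initiation rates and on assumed endorsement of 30-50%. Whether all men are asked about barriers before any dose cannot be confirmed, because the survey appendices are not available.

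**What to change.** In section 11.0:

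- Keep the analysis of unvaccinated men and label it descriptive.
- Add an exploratory table. For each barrier item measured before any dose (at baseline, or at the end of Phase 1 in men with no dose yet), give endorsement in later initiators and in non-initiators, with the arm-adjusted difference and 95% CI. Arm adjustment matters because on the plan's rates about 69-78% of initiators would be in the treatment arm (34.6/49.9 to 40.3/51.8), and answers at the end of Phase 1 may already reflect the messages.
- State that prevalence and difference will be read together when choosing barriers to target, and that with several items some intervals will exclude zero by chance.

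**Cost.** If all men already answer barrier items, this needs a short change of wording and one table. If not, a few questions must be added to an existing survey. Section 9.0 records an incentive change in June 2018 affecting participants already active, so items added after that point would miss earlier enrollees. The lasting downside is wide intervals, so the table can guide but not settle the choice of barriers.

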Data for the in-depth interviews will be collected in person or by phone. Interviews will take place in the privacy of the PI's ([name]) office and will last approximately 45-60 minutes. Participants will be able to skip any questions they are not comfortable answering.

Surveys will include sensitive questions such as questions about sexual behavior. The benefits to collecting data online include increased self-disclosure compared to interviewer-based data collection; convenience for the participant, as he can decide when to complete it; and increased safety, as he can decide when and where it is best to answer these questions. Participants will also be able to skip any questions that make them uncomfortable.

We are sensitive to how the survey experience can affect the validity of the data. All online surveys will be as brief as possible and configured for easy completion on multiple platforms (e.g., cell phone, tablet, laptop). Based on previous research, we estimate that the Step 1 online survey will take approximately 10-15 minutes, the baseline survey will take approximately 15-20 minutes, the immediate post-test survey (end of Phase 1) will take approximately 25-30 minutes, and the end of trial survey will take about 15-20 minutes. The shorter version of the end of trial survey offered to participants who are difficult to reach and out of window will take about 5 minutes. Pop-up surveys (during Phase 2) will take less than one minute to complete.

HPV vaccination status will be verified via the Illinois Comprehensive Automated Immunization Registry (I-CARE) and participants' medical chart. Vaccination status will be confirmed in I-CARE for all RCT participants both before participants begin receiving messages and at the end of the 9-month trial. Pharmacies in the state of Illinois are required to report all vaccinations to the registry,⁵⁷ thus any HPV vaccines administered to participants at a local pharmacy over the course of the 9-month trial will be documented in I-CARE.

Additionally, medical chart data will be sought from those participants who report receiving any doses of HPV vaccine from their primary care physician over the 9-month

PROTOCOL TITLE: txt2protect

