13.0 Withdrawal of Subjects*

The CO-PIs do not anticipate having to a) withdraw subjects from this research without their consent or b) terminate the study early.

Participants may decide to withdraw from the study at any time. No additional data will be collected after a participant withdraws. When a participant shares his intent to withdraw, the investigator will ask if the information already collected can be used or whether it should be destroyed.

PROTOCOL TITLE: txt2protect

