23.0 Local Number of Subjects

We plan to enroll **950 participants total**.

Aim 1 participants will be recruited to assist with the development of the intervention messages:

Step 1: Four online focus groups with 20 participants per group = **80**

Online survey with 250-300 participants = **300**

In-depth interviews with 25-30 participants = **30**

Step 3: Three content advisory teams with 20 participants per team = **60**

Step 5: Beta test will include 20 participants total = **20**

Aim 2, participants will be recruited to pilot test the text messaging-based intervention:

PROTOCOL TITLE: txt2protect

Pilot RCT: We will recruit 230 participants per arm (treatment vs. control) = 460

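### Enrolling 230 per arm leaves 184, not 192, at the plan's own 20% attrition; the power claim survives with the uncorrected chi-square, so this is a wording correction

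*Combined protocol and SAP*

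**What the plan says.** All the sizing is in the Power Analysis paragraph of section 11.0. It hypothesises first-dose uptake of 18-21% in the treatment arm and 6-8% in the control arm. It continues "The comparison of outcomes between arms, with two-sided alpha = 0.05, will have" more than 80% "power for all scenarios with N=192 per condition". It then says "we anticipate an attrition rate of 5-20" per cent and concludes: "Using the most conservative estimate (20%) we will enroll 230 participants per arm to account for attrition". Section 23.0 carries the number forward: "We will recruit 230 participants per arm (treatment vs. control) = 460".

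Four other statements bear on whether attrition reduces the analysed number:

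- Section 11.0, Analysis Strategy: "Intervention efficacy will be assessed using an intent-to-treat approach". The tests are described only as chi-square analyses, with no rule for missing vaccination status.
- Section 9.0, Sources of Materials (repeated in section 25.0): "Vaccination status will be confirmed in I-CARE for all RCT participants", before messages start and at the end of the trial.
- Sections 8.0, 9.0 and 25.0: primary-care doses not found in I-CARE are verified only if the participant reports them and signs a medical release.
- Section 13.0: "No additional data will be collected after a participant withdraws".

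**The concern.** If 192 per arm is the number the power statement needs, enrolment should still leave 192 after the loss the plan calls its most conservative. At that loss, 230 does not. Nor is 20% a remote case: section 8.0 sets 80% nine-month retention as the feasibility threshold, so a trial that just met its own target would retain 184 per arm.

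Two things are at stake. One is whether the claim of more than 80% power still holds with the smaller number. The other is whether a reader can tell which number will be analysed, since the paragraph inflates for attrition without saying whether attrition removes anyone from the vaccination analysis.

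**Working it through.** **Inputs** (section 11.0 unless stated): treatment rate 18% or 21%; control rate 6% or 8%; two-sided alpha 0.05; 192 per arm; attrition 5-20%; enrolment 230 per arm; 1:1 allocation (section 9.0).

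**1. The plan's power statement at 192.** Pooled-variance formula for the uncorrected chi-square, with p̄ the mean of the two rates and d their difference:

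power = Φ{[d − 1.96·√(2p̄(1−p̄)/n)] / √([p₁(1−p₁) + p₂(1−p₂)]/n)}

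For 18% vs 8% and n = 192: d = 0.10 and p̄ = 0.13. The null standard error is √(0.2262/192) = 0.03432 and the alternative standard error is √(0.2212/192) = 0.03394. Then (0.10 − 0.06727)/0.03394 = 0.964, and Φ(0.964) = 83.3%. The other three scenarios are higher, so the claim of more than 80% at 192 reproduces.

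**2. The attrition step.**

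- Needed to keep 192 after a 20% loss: 192 / (1 − 0.20) = 240.
- Left from 230 after a 20% loss: 230 × 0.80 = 184, which is 8 below 192 (8/192 = 4%).
- Likely origin of 230: 192 × (1 + 0.20) = 230.4. The plan shows no formula, so this is an inference; the mismatch does not depend on it.
- Largest loss at which 230 still leaves 192: 1 − 192/230 = 16.5%.

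**3. Power at the number left** (same formula):

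| Scenario | n = 184 | n = 192 | n = 230 |
|---|---|---|---|
| 18% vs 8% | 81.7% | 83.3% | 89.3% |
| 18% vs 6% | 94.6% | 95.4% | 97.9% |
| 21% vs 8% | 94.6% | 95.4% | 97.9% |
| 21% vs 6% | 98.9% | 99.2% | 99.8% |

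For 18% vs 8%, power reaches 80% at 177 per arm, that is, at 1 − 177/230 = 23.0% attrition.

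**4. How the loss is handled** (18% vs 8%, 20% loss):

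- Lost participants excluded, n = 184: 81.7%.
- All 230 ascertained through I-CARE at the planned rates: 89.3%.
- All 230 analysed, lost participants counted as unvaccinated. Assuming equal loss in both arms, unrelated to vaccination, with none of their doses captured, the rates become 0.8 × 18% = 14.4% and 0.8 × 8% = 6.4%. Power is 80.5%.

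**5. Version of the test** (18% vs 8%, exact enumeration):

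| Test | n = 184 | n = 192 |
|---|---|---|
| Uncorrected Pearson | 82.9% | 84.2% |
| Yates-corrected | 78.1% | 80.1% |
| Fisher's exact | 78.1% | 80.1% |

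For Fisher's test, 191 per arm gives 79.95% and 192 gives 80.12%, so 192 is where that test crosses 80%. The plan's 192 may have come from such a calculation, but it does not say so. With Yates or Fisher, the other three scenarios stay above 93% at 184.

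**The case against.** The strongest reply is that attrition may not reduce the analysed number at all. The analysis is intent-to-treat and I-CARE is to be checked for every randomised participant, so someone who skips the nine-month survey still has a registry outcome. Only those who withdraw stop contributing data. On that reading all 230 per arm are analysed and worst-case power is 89.3%. The band in which 192 is missed is also narrow, 16.5% to 20%, and the retention the plan cites from similar studies, up to 85-95%, would leave at least 195 (230 × 0.85 = 195.5).

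Much of this stands. It is why 184 is conditional and why the point is minor. It does not rescue the sentence. Registry ascertainment is incomplete by design, because some primary-care doses depend on self-report and a signed release. And the plan itself inflates for attrition: if attrition removes participants, 230 is too few to keep 192 at 20%; if it removes nobody, no inflation was needed and power should be quoted at 230.

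A second objection is that naming the uncorrected test picks the version under which the claim survives. It is the ordinary form of the chi-square test the plan already specifies, but the reassurance about enrolment holds only with that test.

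**Conclusion.** The concern holds, as a minor arithmetic error. Enrolling 230 per arm does not offset 20% attrition from 192. It leaves 184 if lost participants are excluded, a shortfall of 8 per arm, and there is no shortfall at 16.5% attrition or less. The claim of more than 80% power remains true in all four scenarios with the uncorrected Pearson chi-square, with a minimum of 81.7% at 184 per arm. It would fail only for 18% vs 8%, at 78.1%, if a Yates correction or Fisher's test were used and lost participants were excluded. The conclusion takes the plan's uptake rates as given and assumes the same loss in each arm.

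**What to change.** Replace the end of the power paragraph with text along these lines:

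> With 230 enrolled per arm, a 20% loss leaves 184 per arm if participants lost to follow-up are excluded, giving about 82% power for 18% vs 8% (uncorrected Pearson chi-square, two-sided 0.05). An analysed size of 192 per arm corresponds to attrition of at most 16.5%.

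Then state the intent-to-treat rule for missing vaccination status and keep only the power figure that matches it: about 82% if lost participants are excluded, about 89% if all 230 are ascertained through I-CARE, or about 80% if a lost 20% are counted as unvaccinated (with the assumptions of that calculation stated). Name the uncorrected Pearson chi-square in the Analysis Strategy.

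The cost is wording only. Worst-case power, which the plan does not quote beyond more than 80%, moves from a computed 83.3% to 81.7% if lost participants are excluded. No extra enrolment is needed with that test. If the sponsor intends a Yates-corrected or Fisher's test and excludes lost participants, keeping 80% for 18% vs 8% would take the full 192 analysed, hence 240 enrolled per arm (480 in total, not 460).
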